9 LIST OF TABLES AND TABLE SHELLS

For the table shells and the corresponding list of tables, listings and figures of final analysis please refer to the final version of B7451089 Mockups.docx.

11 APPENDICES

11.1 APPENDIX 1: DATA DERIVATION DETAILS

EASI-75-responder: Percentage of patients with 75% reduction from baseline in EASI EASI-90-responder: Percentage of patients with 90% reduction from baseline in EASI SCORAD-75-responder: Percentage of patients with 75% reduction from baseline Abrocitinib responder: EASI-75-responder and/or SCORAD-75-responder and/or IGA 0/1

Number of days with topical treatment use (TCS, TCI): Date of first topical treatment – date of last topical treatment + 1

Number of days with emollients use: Date of first emollients use – date of last emollients use + 1

 $\underline{Days\ of\ AD\text{-treatment:}}\ Date\ of\ last\ AD\ treatment-date\ first_AD\text{-treatment}+1$

Age [years]: Year of informed consent – year of birth

Age at initial diagnosis of AD [years]: year of initial diagnosis – year of birth

Percentage change to baseline: (score at respective visit – score at baseline)/score at baseline*100

Information of additional documentation timepoints will be added to the information of the next scheduled visit and analyzed at the scheduled visit.

PROs and other questionnaires referring to additional documentation timepoints will not be analyzed but may be of interest if the course of individual patients is considered in more detail.

PROs will be assigned to the month/scheduled visit according to the time windows given below.

A1.1 Definition and use of visit windows in interim analysis

Visit Label	Endpoint	Definition [Day window]
Enrolment	All	1
Month 1	All	2 to 44
Month 3	All	45 to 105
Month 6	All	106 to 210
Month 9	All	211 to 301
Month 12	All	302 to 393

PFIZER CONFIDENTIAL

CT24-WI-GL03-RF02 2.0 Non-Interventional Statistical Analysis Plan For Primary Data Collection Study 01-Jun-2020
Page 38 of 39

A1.2 Further definition of endpoints

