9.1.1. Endpoints

Primary Endpoints:

- a. Response based on achieving the **IGA** of clear (0) or almost clear (1) (on a 5-point scale) at month 3.
- b. Response based on achieving the **EASI-75** at month 3.

Secondary Endpoints:

Physician's global assessment of efficacy parameters (assessed at all visits [except for month 3 for a. and b.]):

- a. Response based on achieving the **IGA** of clear (0) or almost clear (1) (on a 5-point scale).
- b. Percentage of patients with EASI-75 response compared to baseline.
- c. Response based on achieving the EASI-90.
- d. Response based on achieving the **IGA** of clear (0) or almost clear (1) and a reduction from baseline of ≥ 2 points.
- e. Percentage change of **IGA** compared to baseline.
- f. Percentage change of **SCORAD** compared to baseline.
- g. Absolute **EASI** values over time.
- h. Percentage change of EASI compared to baseline.
- i. Absolute change of **IGA** compared to baseline.

Patient's assessment of efficacy and quality parameters (assessed at all visits):

- a. Response based on achieving at least 4 points improvement of Pruritus **NRS** from baseline.
- b. Change of Peak-Pruritus NRS over time.
- c. Change of **POEM** from baseline.
- d. Change of MOS from baseline.
- e. Change of DLQI from baseline.

- f. Change of HADS from baseline.
- g. Change of EuroQol five-dimensional-five level (EQ-5D-5L) from baseline.
- h. Patient's satisfaction with treatment measured by PBI.
- i. Patient's expectation of treatment measured as PBI at baseline.
- j. Number of days with topical-treatment use (TCS, TCI).
- k. Number of days with emollients use.

Explorative Endpoints:

Treatment characteristics (assessed at all visits):

- a. Concomitant treatments.
- b. Tolerability of abrocitinib and reasons for discontinuation.
- c. Dosage of abrocitinib.
- d. Compliance with abrocitinib treatment.

Patient characteristics assessed at baseline visit only (except for c., f., g., and h. with additional assessment at subsequent visits):

- a. Demographic data of patient (age, sex, weight, occupation, alcohol/smoking, family history).
- b. Clinical history of AD treatment before non-interventional study start.

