Number of absent days at work/study due to AD one year before start of treatment with Abrocitinib (first visit) and since the last visit	X	X	X	X	X	X

^{*} This includes patients who discontinued treatment with Abrocitinib.

Study period based on routine visits	Baseline (Enroll ment)	Month 1	Month 3	Month 6	Month 9	Month 12 End of Study (EoS)
(regardless of Abrocitinib treatment status*)						
Reasons for start of therapy with Abrocitinib	X					
Reasons for discontinuation of therapy with Abrocitinib		X	X	X	X	X
Compliance with Abrocitinib treatment		X	X	X	X	X
Dosage of Abrocitinib used	X	X	X	X	X	X
Reasons for prescribed dosage	X	X	X	X	X	X
Type and results of laboratory check controls	X	X	X	X	X	X
Adverse events		X	X	X	X	X
Concomitant treatment AD specific (type and dosage)	X	X	X	X	X	X
Number of days with topical- treatment use (TCS, TCI) & days with emollients use three months before start of treatment with Abrocitinib (first visit) and since the last visit (regardless of Abrocitinib treatment status*	X	X	Х	X	X	X
Concomitant (non-AD) treatment	X					
SCORAD	X	X	X	X	X	X
EASI	X	X	X	X	X	X

^{*} This includes patients who discontinued treatment with Abrocitinib.

Study period based on routine visits	Baseline (Enroll ment)	Month 1	Month 3	Month 6	Month 9	Month 12 End of Study (EoS)
IGA	X	X	X	X	X	X
Pruritus-NRS	X	X	X	X	X	X
PP-NRS	X	X	X	X	X	X
DLQI	X	X	X	X	X	X
POEM	X	X	X	X	X	X
MOS	X	X	X	X	X	X
PBI	X	X	X	X	X	X
EQ-5D-5L	X	X	X	X	X	X
HADS	X	X	X	X	X	X

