9.2.4.6. Concomitant Treatment for Atopic Dermatitis

At each visit (Visit 1-6) dose and type of concomitant treatment will be documented. At baseline visit the number of days with topical-treatment use (TCS, TCI) and emollients use three months before start of treatment with abrocitinib (first visit) and at each subsequent visit number of days with topical- treatment use (TCS, TCI) and emollients use days since the last visit (follow-up visits) will be assessed.

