Clinical history (Herpes simplex, eczema herpeticum, herpes zoster)	X					
Renal and/or liver impairment	X					
Vaccination status (Herpes zoster, Covid- 19, Influenza, Varicella)	X					X
Age at initial diagnosis of AD	X					

Study period based on routine visits	Baseline	Month	Month	Month	Month	Month
routine visits	(Enroll ment)	1	3	6	9	12
						End of Study (EoS)
Previous treatments for diagnosed AD	X					
Current comorbidities	X					
If positive anamnesis at baseline exists: Improvement of asthma symptoms from baseline						X
If positive anamnesis at baseline exists: Improvement of allergic rhinitis symptoms from baseline						X
If positive anamnesis at baseline exists: Improvement of polyposis nasi symptoms from baseline						X
If positive anamnesis at baseline exists: Improvement of alopecia areata from baseline						X
If positive anamnesis at baseline exists: Improvement of prurigo nodularis from baseline						X
If positive anamnesis at baseline exists:						X

[figure not shown]
Study period based on routine visits	Baseline (Enroll	Month	Month	Month	Month	Month
routine visits	ment)	1	3	6	9	12
						End of Study (EoS)
Improvement of hand eczema from baseline						
Number of flares during the last 12 months (first visit) and since the last visit (regardless of abrocitinib treatment status*)	X	X	X	X	X	X
Number of hospitalizations due to AD during the last 12 months (first visit) and since the last visit (regardless of abrocitinib treatment status*)	X	X	X	X	X	X
Number of absent days at work/study due to AD one year before start of treatment with abrocitinib (first visit) and since the last visit (regardless of abrocitinib treatment status*)	X	X	X	X	X	X
Reasons for start of therapy with abrocitinib	X					
Reasons for discontinuation of therapy with abrocitinib		X	X	X	X	X

Study period based on	Baseline	Month	Month	Month	Month	Month
routine visits	(Enroll ment)	1	3	6	9	12
						End of Study (EoS)
Compliance with abrocitinib treatment		X	X	X	X	X
Dosage of abrocitinib used	X	X	X	X	X	X
Reasons for prescribed dosage	X	X	X	X	X	X
Type and results of laboratory check controls	X	X	X	X	X	X
Adverse events		X	X	X	X	X
Concomitant treatment AD specific (type and dosage)	X	X	X	X	X	X
Number of days with topical- treatment use (TCS, TCI) & days with emollients use three months before start of treatment with abrocitinib (first visit) and since the last visit (regardless of abrocitinib treatment status*)	X	X	X	X	X	X
Concomitant (non-AD) treatment	X					
SCORAD	X	X	X	X	X	X

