6.3 OTHER ENDPOINTS

Variable	Role	Data source(s)	Operational definition	
AD-treatment with abrocitinib and/or without topicals – total days	Exposure, Potential confounder, potential subgroup identifier	Case records	Date of last treatment – date of first treatment +1 Summary statistics (n, mean, median, standard deviation, minimum and maximum)	
AD-treatment with abrocitinib and/or without topicals – stratified by abrocitinib dose Exposure, Potential confounder, outcome, potential subgroup identifier		Case records	Date of last treatment – date of first treatment +1 Summary statistics (n, mean, median, standard deviation, minimum and maximum) stratified by the abrocitinib dose most often applied during the study	
Age (Year of birth)	Baseline characteristics, potential confounder, potential subgroup identifier	Case records	Age=year of IC – year of birth Summary statistics (n, mean, median, standard deviation, minimum and maximum)	
Sex	Baseline characteristics, potential confounder, potential subgroup identifier	Case records	Frequency analysis	
Height Baseline characteristics		Case records	Summary statistics (n, mean, median, standard deviation, minimum and maximum)	
Weight Baseline characteristics		Case records	Summary statistics (n, mean, median, standard deviation, minimum and maximum)	
Highest level of education	Baseline characteristics, potential confounder	Case records	Frequency analysis	
Ethnicity Baseline characteristics		Case records	Frequency analysis	

Occupational status	Baseline characteristics	Case records	Frequency analysis
Alcohol consumption status	Baseline characteristics, potential confounder	Case records	Frequency analysis
Insurance type	Baseline characteristics	Case records	Frequency analysis
Presence of family history of atopic diseases	Baseline characteristics, potential confounder, potential subgroup identifier	Case records	Frequency analysis
History of herpes simplex and/or eczema herpeticum and/or herpes zoster	Baseline characteristics	Case records	Frequency analysis
Vaccination status (Herpes zoster, Covid-19, Influenza Varicella)	Baseline characteristics	Case records	Frequency analysis
Age at initial diagnosis of AD	Baseline characteristics, potential confounder	Case records	Age at initial diagnosis =year of initial diagnosis – year of birth 1. Summary statistics (n, mean, median, standard deviation, minimum and maximum) 2. Categorical: < 12 y, 12-<18 y and ≥ 18 y

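### The SAP derives days of topical and emollient use as first date minus last date plus 1: the sign is reversed, and the corrected formula still gives a calendar span instead of a count of use-days

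*SAP*

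**What the plan says.** SAP Appendix 1 (Section 11.1) derives the topical variable as "Date of first topical treatment – date of last topical treatment + 1" and the emollient variable as "Date of first emollients use – date of last emollients use + 1". The secondary-endpoint table in SAP Section 6.1 has the same order for both, so there are four entries in all. For abrocitinib exposure, SAP Section 6.3 uses the opposite order, "Date of last treatment – date of first treatment +1", and Appendix 1 does the same for AD treatment.

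Protocol Section 9.1.1 lists secondary endpoint j as "Number of days with topical-treatment use (TCS, TCI"), with the matching emollient endpoint as k. Both stand under a heading that reads "assessment of efficacy and quality parameters (assessed at all visits"). The schedule in Protocol Section 9.2.3.2 asks for "days with emollients use three months before start of treatment with Abrocitinib (first visit) and since the last visit". Section 9.2.4.6 confirms the follow-up item: "number of days with topical- treatment use (TCS, TCI) and emollients use days since the last visit". The schedule in SAP Section 1.1 repeats the requirement: "days with emollients use three months before start of treatment with abrocitinib (first visit) and since the last visit".

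SAP Section 8.2.3 (rows 24 and 25) plans summary statistics and Mann-Whitney-U subgroup tests on the two variables, with missing data excluded.

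**The concern.** There are two separate faults.

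- **Sign.** With the dates subtracted in the written order, any inclusive span longer than two days is negative, and a longer span gives a lower value. This is easy to see and can be undone.
- **Span instead of count.** A programmer who meets negative days will probably swap the dates. The output will then look plausible, but it measures the time from first to last use. Topicals and emollients may be used intermittently, and use-days cannot be recovered from a span.

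Two gaps follow from the same derivation. The rows for these variables give no time point, whereas most other rows in the Section 6.1 secondary-endpoint table do. It is therefore open whether the result is one value per visit or one per patient, and whether the pre-treatment period is included. Also, a patient with no topical use has no first or last date. The SAP gives no rule for that case, so such a patient could be dropped as missing, whereas a count would record 0.

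At stake is whether two named secondary endpoints report what their labels say. The study is descriptive, so these summaries are the result.

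**Working it through.** **Inputs.** The two SAP formulas (Section 6.1, Appendix 1), the SAP exposure formula (Section 6.3), and the visit target days 1, 30, 91, 182, 273 and 365 (SAP Section 1.1). The documents state no numerical result for these variables, so there is no figure to reproduce. They also give no pattern of topical use; the patterns below are assumptions.

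**Step 1: sign.** Let S be the inclusive span, so last − first = S − 1.

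- As written: first − last + 1 = −(S − 1) + 1 = 2 − S.
- Reversed: last − first + 1 = S.

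| Span S (days) | As written (2 − S) | Reversed (S) |
|---|---|---|
| 1 | 1 | 1 |
| 2 | 0 | 2 |
| 31 | −29 | 31 |
| 90 | −88 | 90 |

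Because 2 − S exactly reverses the ranks of S, the two-sided Mann-Whitney p-value is the same for both. The direction of the difference and the summary statistics are not.

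**Step 2: span against count, sign corrected.** Use-days over 90 days = 90 × (days per week) / 7; ratio = 90 / use-days.

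| Assumed use | Use-days | Span | Ratio |
|---|---|---|---|
| Daily | 90 | 90 | 1.0 |
| Every other day | 45 | 90 | 2.0 |
| Three times a week | 90 × 3/7 = 38.6 | 90 | 2.3 |
| Twice a week | 90 × 2/7 = 25.7 | 90 | 3.5 |
| Once a week | 90 × 1/7 = 12.9 | 90 | 7.0 |

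Courses behave in the same way: two seven-day courses on days 1–7 and 85–91 are 14 use-days but a span of 91.

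**Step 3: ordering.** Patient A uses a topical twice a week over 90 days (about 26 use-days, span 90). Patient B uses it daily for 31 days (31 use-days, span 31). The span puts A far above B; the count puts B above A. Span and count can therefore disagree in rank-based subgroup tests as well as in scale.

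**Step 4: recall intervals.** Differences between target days are 30 − 1 = 29, 91 − 30 = 61, 182 − 91 = 91, 273 − 182 = 91 and 365 − 273 = 92. Constant twice-weekly use gives counts of about 8, 17, 26, 26 and 26, but 2/7 = 28.6% of days in every interval. Raw counts are therefore not comparable across visits without the interval length. Visits are not mandatory, so actual intervals will differ from these.

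**The case against.** The strongest reply is that Protocol Table 2 leaves the operational definition of this variable to the SAP, and Protocol Section 9.7 lets the SAP modify the protocol's plans, requiring an amendment only for major changes to primary endpoints. This stands in part: the protocol names and schedules a count, but does not give a full operational definition. It does not rescue the formula. The SAP announces no change, keeps the label of days of use, and repeats the per-visit count in its own schedule, so the conflict exists within the SAP alone.

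Second, the reversed order is evidently a slip that the first table run would expose. That is fair, and it is why the span is the more serious half.

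Third, the size of the span error rests on assumed patterns, and the range includes no error at all for daily use. That also stands: the ratios illustrate what can happen and do not estimate the bias in this study.

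Fourth, neither the eCRF nor the table shells are among the documents. The eCRF may hold dates, and the shells may state time points. This limits what can be said about cost and about the full specification, but not about the SAP text.

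**Conclusion.** The concern holds. As written, the formula returns 2 minus the inclusive span in all four places, which is negative beyond two days and contradicts the SAP's own order for treatment duration. With the sign corrected, it returns a calendar span that equals the scheduled count only for daily, uninterrupted use; for the assumed intermittent patterns over 90 days it is 2.0 to 7.0 times too large. The sign and the definitional mismatch follow from the text alone. The size of the overstatement depends on use patterns that the documents do not give. The consequence is confined to two descriptive secondary endpoints and their exploratory subgroup comparisons. This should be corrected before the analysis is programmed.

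**What to change.** - In the two entries in SAP Section 6.1 and the two in Appendix 1, replace the date formula with the recorded number of use-days per recall interval: the three months before abrocitinib at baseline, then the time since the previous visit.
- State the time points, and whether any total over follow-up is reported and excludes the pre-treatment period. State that no use counts as 0.
- Add the same time points to rows 24 and 25 of SAP Section 8.2.3, which contain no date formula of their own, and to the table shells.
- If a first-to-last span is kept as a description, label it as a span and write it as last − first + 1.
- Advisable where visits are compared or counts are summed over unequal follow-up: also report use-days as a percentage of days in the interval. Change from baseline is optional; the SAP does not plan it for these variables.

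The cost is a small text edit using data that the protocol already schedules. That the eCRF stores the counts is inferred from the protocol's schedule, Section 9.2.4.6 and Section 9.4, and should be confirmed first. If it does not, the endpoint cannot be derived as named, and the SAP should say so.

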DLQI	Secondary outcome variable	Case records	 Percentage of patients achieving at least 4 points improvement of DLQI from baseline Summary statistics (n, mean, median, standard deviation, minimum and maximum) of the score at each point in time as well as the percentage change to baseline Percentage of patients with DLQI ≤1
POEM	Secondary outcome variable	Case records	Summary statistics (n, mean, median, standard deviation, minimum and maximum) of the score at each point in time as well as the percentage change to baseline
MOS-Sleep scale	Secondary outcome variable	Case records	Summary statistics (n, mean, median, standard deviation, minimum and maximum) of the

scales at each point in time as well as the percentage change to baseline Summary statistics (n, mean, median, standard deviation, minimum and maximum) of the Patient single items and the total score at Case records Benefit Secondary outcome variable each appropriate point in time as Index well as the percentage change to visit 2 (about one months after baseline) Patient Expectation As measured by PBI questionaire s on and (refer to line above; expectation Satisfaction PBI at baseline, satisfaction PBI at Secondary outcome variable Case records with all points in time after baseline) abrocitinib treatment Summary statistics (n, mean, median, standard deviation. minimum and maximum) of the EQ-5D-5L VAS and EQ-5D index score at Secondary outcome variable Case records each point in time as well as the percentage change to baseline Summary statistics (n, mean, median, standard deviation, minimum and maximum) of the **HADS** anxiety score and depression score Secondary outcome variable Case records at each point in time, respectively as well as the percentage change to baseline Number of Date of first topical treatment – date days with of last topical treatment + 1 topical treatment Secondary outcome variable Case records Summary statistics (n. mean. median, standard deviation, use (TCS, TCI) minimum and maximum) Date of first emollients use – date of last emollients use + 1 Number of days with emollients Secondary outcome variable Case records Summary statistics (n, mean, use median, standard deviation, minimum and maximum)

Analysis of questionnaires

Questionnaire	Analysis
SCORAD	Scoring Atopic dermatitis: validated scoring index for AD for severity, combining A: extent (0-100), B: severity (0-18) and C: subjective symptoms (0-20) based on itching and sleep deprivation,

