	question, 0 to 3 points are given, whereby 3 points indicate the greatest possible impairment of the QoL in the queried area. The sum of scores ranges from 0 to 30, with higher scores indicating greater impairment of quality of life. If one question is unanswered it is scored with 0. If more than one question is not answered the score cannot be determined.
	(https://www.cardiff.ac.uk/medicine/resources/quality-of-life-questionnaires/dermatology-life-quality-index)
MOS	The Medical Outcomes Study Sleep Scale (MOS-Sleep) includes 12 items assessing sleep disturbance (questions 1, 3 (R-reversed), 7 (R) and 8(R)), sleep adequacy (questions 4 (R) and 12 (R)), somnolence (questions 6 (R), 9(R) and 11 (R)), quantity of sleep (question 2), snoring (question 10 (R)), and awakening short of breath or with a headache (question 5 (R)) whereat question 1 scores from 1 (0-15 min) to 5 (>60 min) and questions 3 to 12 from 1 (all of the time) to
	5 (none of the time). 1 is recoded to 0, 2 to 25, 3 to 50, 4 to 75 and 5 to 100. If the answers have to be reversed 1 is recoded to 100, 2 to 75, 3 to 50, 4 to 25 and 5 to 0. The scores represent the average for all items in the scale that were answered, i.e. missing data are not taken into account.
PBI	Measurement of patient defined treatment benefits according to German and international standards, contains two one-sided questionnaires which are to be completed by the patient before and after receiving a treatment. A total of 25 possible treatment goals are evaluated on an
	importance scale from 0 ("not at all") to 5 ("very"). "does not apply to me" will be coded as "0". The analysis will include: a) means and standard deviations of all items ("does not apply to me" is
	coded as 0 for this single-item analysis of the PBI) b) for each item the percentage of the response "does not apply to me" c) for each item the percentage of responses with high agreement (quite or very) d) percentage of missing values The weighted index value, the actual "Patient Benefit Index"
	(PBI), is calculated by multiplying the achieved benefits (respective PBI after baseline) with the importance of the respective needs prior to therapy (PBI at baseline), dividing these products by the sum of all importance items (PBI at baseline), and summing them up for all items. The total PBI score ranges from 0 (no benefit) to 5 (maximal benefit).

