EQ-5D-5L	Generic instrument for measuring quality of life, including health benefits and health status on a visual analogue scale (VAS), using the five dimensions (mobility, self-care, usual activities, pain/discomfort, anxiety/depression). The health status is given as a sequence of the five diemnsions. Missing values are coded as "9". However the EQ-5D index score can only be determined according to the EQ-5D-5L German values if all 5 health dimensions have been specified.
HADS	The Hospital Anxiety and Depression Scale is a 14-item measure that identifies anxiety (7 items) and depression (7 items) among adults who are physically ill with lower scores indicating lower levels of anxiety and depression. Scoring for each item ranges from 0 to 3, with 3 denoting highest anxiety or depression level. For both subscales the score is derived by summing up the respective 7 items.

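### Change in six patient-reported scales is defined only as percentage change, which is undefined at a baseline of 0 and has an upward-biased mean

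*SAP*

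**What the plan says.** Protocol 9.1.1 words the patient-reported endpoints as plain change, for example "Change of MOS from baseline" and "Change of HADS from baseline". POEM, DLQI and EQ-5D-5L are worded alike, and PP-NRS is a change over time. In the physician-assessed list of the same section, percentages are named where they are wanted, as in "Percentage change of EASI compared to baseline"; IGA and SCORAD also have a percentage entry, and IGA has an absolute-change entry as well.

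SAP 6.1 summarises POEM and DLQI by statistics "of the score at each point in time as well as the percentage change to baseline", and treats PP-NRS, MOS, HADS and EQ-5D-5L in the same way. In SAP 8.2.3 the rows for change in these six scales carry the percentage formula and a Mann-Whitney test for subgroups. Appendix 1 (SAP 11.1) has one derivation of change: "score at respective visit – score at baseline)/score at baseline*100".

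SAP 6.1 also sets the scoring. For HADS: "Scoring for each item ranges from 0 to 3, with 3 denoting highest anxiety or depression level", summed over seven items per subscale. For MOS: "1 is recoded to 0, 2 to 25, 3 to 50, 4 to 75 and 5 to 100", with the reverse coding for most items. SAP 7 excludes imputation in general. Neither document says what to do when the baseline is 0.

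**The concern.** The protocol separates plain change from percentage change, and the SAP turns the first into the second without comment. The ratio causes three problems on bounded scales that start at 0.

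- It does not exist for a patient whose baseline is 0.
- It is asymmetric. Improvement is bounded at -100%, while a rise from 1 to 2 is already +100%. A few patients with low baselines can dominate the mean.
- It ranks patients differently from a change in points when their baselines differ, and the subgroup tests work on those ranks.

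At stake are the descriptive results on anxiety, depression, sleep, itch and quality of life, and the exploratory subgroup comparisons of them.

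**Working it through.** The documents give no baseline distribution for these scales and no figure to reproduce. The check applies the SAP formula, % = 100 × (visit - baseline)/baseline, beside the simple difference, visit - baseline.

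**1. Is 0 a possible baseline?** From SAP 6.1: HADS subscale 7 × (0 to 3) = 0 to 21; DLQI 0 to 30; POEM 7 × (0 to 4) = 0 to 28; PP-NRS 0 to 10; recoded MOS scales 0 to 100. So yes on each. The single-item MOS scales (snoring; waking short of breath or with headache) are 0 for anyone who answers that it never happens.

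**2. Which patients are lost?** Where 0 is the best score, those at 0 can only stay or worsen, so losing them favours improvement. MOS sleep adequacy (questions 4 and 12, reversed) gives 0 to the worst answer, so the loss works the other way there. Constructed DLQI data 0→6, 0→5, 10→5, 12→6, 15→8:
- Difference, all five: (6 + 5 - 5 - 6 - 7)/5 = -1.4 points.
- Percentage, three computable patients: (-50 - 50 - 46.7)/3 = -48.9%.

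**3. Can the mean reverse?** Constructed HADS data 1→5, 8→5, 10→6, 12→8:
- Mean difference: (4 - 3 - 4 - 4)/4 = -1.75 points (better).
- Mean percentage: (400 - 37.5 - 40 - 33.3)/4 = +72.3% (worse).
- Median percentage: (-37.5 - 33.3)/2 = -35.4% (better).

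**4. How large is the bias under assumed distributions?** Assumed: a 0-21 scale; each patient's underlying level is gamma distributed with mean 4, 5 or 7 and shape 1.5, 2 or 3; two Poisson visits capped at 21; 400,000 simulated patients.

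| Baseline mean | Baseline 0 | Mean %, no change | Mean %, true 20% fall | Median %, no change / 20% fall |
|---|---|---|---|---|
| 4 | about 14% | +16 | -7 | 0 / -25 |
| 5 | about 8% | +19 | -5 | 0 / -25 |
| 7 | about 3% | +20 | -4 | 0 / -20 |

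The true falls are 0.8, 1.0 and 1.4 points (20% of 4, 5 and 7).

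A second set of assumptions used a rounded gamma baseline with mean 4, 6 or 8 (SD 3.5, 4, 4), a shift of -1 or -2 points, and SD of change 2 to 4. It gave about 7%, 0.8% and 0% zero baselines, or about 55, 6 and 0 of 750 patients. The mean reversed sign in 1 of 18 scenarios: baseline mean 4, shift -1, SD of change 4, with mean difference -0.16 points and mean percentage +6.3%.

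**5. Do rank tests avoid the problem?** Constructed example with five patients per subgroup, for illustration only:
- A: baselines 3, 3, 4, 4, 5; falls 2, 2, 2, 3, 3 points, or 67, 67, 50, 75, 60%.
- B: baselines 12, 14, 15, 16, 18; falls 4, 5, 5, 5, 6 points, or 33, 36, 33, 31, 33%.

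In points every B patient improves more than every A patient. In percent every A patient improves more. Mann-Whitney gives p of about 0.01 both times, in opposite directions.

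**The case against.** The case for leaving the SAP alone has real substance.

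- **The SAP may do this.** Protocol 9.3 leaves operational definitions to the SAP, and 9.7 lets it modify the plan, with an amendment only for major changes to the primary endpoints or their analysis. A reader might infer a protocol breach or undelivered endpoints; the documents do not support that. What stands is that the change is neither flagged nor justified.
- **Information in points is not absent.** Every scale has its score summarised per visit, and Pruritus-NRS, PP-NRS and DLQI have responder rates for at least 4 points improvement. But visits are optional, so means at different visits may come from different patients, and four of the six scales have no within-patient measure in points.
- **The median is reported.** Each patient's percentage has the same sign as the difference, so the median does not reverse in the simulations. The mean is reported beside it and is the biased figure.
- **Zero baselines are not said to be excluded.** The entry in SAP 8.2.3 concerns missing data. Reading it as a rule for undefined ratios is inference; the SAP is silent.
- **Mann-Whitney uses ranks.** This limits the effect of extreme ratios but not the re-ordering in step 5.
- **The table shells are a separate file.** They might hold more, but the SAP text does not define it.

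**Conclusion.** The point holds. All six changes are defined only by a ratio that fails at a valid baseline and whose mean is pulled upward by low baselines.

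The size depends on assumptions, because the documents give no baseline data. Across both sets of assumptions, between about 0% and 14% of patients start at 0. In the gamma-Poisson set the mean percentage change is about +16% to +20% with no true change, and about -4% to -7% with a true 20% fall.

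Two stronger readings are tempting and not supported. One is that the results would generally show worsening when patients improved: reversal affects the mean, in 1 of 18 scenarios, and not the median. The other is that the lost patients are always those who can only worsen: MOS sleep adequacy is the opposite. Nothing here relies on zero or negative EQ-5D index values, since the value set is not in the documents.

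This should be fixed, but it is not critical. The endpoints are secondary and descriptive, the subgroup tests are exploratory, and both primary endpoints (IGA 0/1 and EASI-75 at month 3) are unaffected.

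**What to change.** In SAP 6.1, 8.2.3 and Appendix 1, define change for PP-NRS, POEM, each MOS scale, DLQI, HADS anxiety, HADS depression, the EQ-5D index and the VAS as score at visit minus score at baseline. Use it for the summaries and the subgroup comparisons.

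Keep percentage change for IGA, SCORAD and EASI, because Protocol 9.1.1 lists it for all three.

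If percentage change of a patient-reported scale is kept as supplementary, report its median and the number of patients with baseline 0, and state how they are handled.

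The cost is SAP wording, one extra derivation and some extra table output, with these changes shown in points. No new data are needed. Making the change before database lock avoids choosing a zero-baseline rule after the results are known.
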